### 13.4. Patient Screening Log

A record listing all patients entered into the study, as well as those considered for entry into the study and subsequently excluded, must be maintained by the Investigator. Patients excluded from the study will have the reason for exclusion recorded on the Patient Screening Log (or other similar document).

### 13.5. **Drug Dispensing Inventory**

Study center personnel will maintain adequate records of the receipt, dispensing, and disposition of all study drug that the Sponsor ships to the site. Records will be maintained, either on a form to be provided by the Sponsor or on a reasonable facsimile authorized for use by the Sponsor, and should include appropriate dates, quantities received, quantities dispensed, lot number (or kit number), disposition details, and the identification code of the patient who received the study drug.

The Investigator agrees to administer study drug only to patients under his/her personal supervision. The Investigator will not supply study drug to any person not authorized to receive it.

### 13.6. Handling and Disposal of Investigational Drug

Study drug should be stored in a secure location, under the indicated conditions (see **Section 5**; Investigational Drug). After study drug is prepared for delivery and administered, the health care professional will maintain an inventory of all used vials of study drug, after which, with authorization from the Sponsor, all such supplies may be destroyed in an appropriate manner according to institutional policy. Destruction of such supplies will be documented. Information regarding the number of vials utilized for each patient, as well as the dose of study drug administered to the patient, will be recorded on the appropriate drug inventory form.

Periodically throughout and at the conclusion of the study, unused vials of study drug will be inventoried by a representative of the Sponsor (or designee). At the completion of this trial, all

unused study materials MUST be returned to the Sponsor (or designee), unless otherwise authorized in writing.

### 13.7. Recording and Processing of Data

Clinical trial data for this study will be captured in an electronic format. Electronic data capture (EDC) services will be provided by a vendor to be determined by the Sponsor. The Investigator agrees to provide all information requested on the electronic case report forms (eCRF) in an accurate manner according to instructions provided. Electronic CRFs are designed for computer processing and analysis. All data must be carefully entered to permit meaningful interpretation. Corrections to entered data will be tracked within the EDC system. Data must be entered onto eCRFs in a timely fashion.

An eCRF is required to be submitted for every patient who receives any amount of study drug. This includes submission of retrievable data on patients who withdraw before completion of the study. Prior to submission, eCRFs must be reviewed for completeness and accuracy, and signed and dated where indicated, by either the Principal Investigator or a physician Subinvestigator whose name is listed on Form FDA 1572 for this study.

# 13.8. Source Document Requirements

The Investigator will maintain adequate and accurate records for each patient treated with study drug. Source documents such as hospital, clinic or office charts, laboratory reports, radiology and pathology reports, pharmacy records, study worksheets, and signed informed consent documents, must completely reflect the nature and extent of the patient's medical care, must be included in the Investigator's files along with patient study records, and must be available for source document verification against entries in the eCRF.

The Sponsor (or designee) will check eCRF entries against source documents according to the guidelines of Good Clinical Practice. The consent form will include a statement by which patients allow the Sponsor (or designee), as well as authorized regulatory agencies, to have direct access to source data that support data on the eCRF (e.g., patient medical files, appointment books, original laboratory records, etc.). The Sponsor (or designee), bound by confidentiality and privacy regulations, will not disclose patient identities or personal medical information.

# 13.9. **Laboratory Reports**

Prior to initiation of this study, the Investigator must supply the Sponsor (or designee) with the normal laboratory values for the laboratories to be utilized; specifically, the normal laboratory values for analytes required to be measured, per protocol, are to be supplied. The corresponding laboratory certification number must also be noted, and a copy of the Director's curriculum vitae provided.

Laboratory safety evaluations must be performed at the intervals specified. If unexplained laboratory abnormalities occur, corroborative tests will be performed until the laboratory abnormality has resolved, returned to baseline status, and/or adequate explanation of the abnormality has been provided.

Copies of any additional records pertinent to the study (e.g., laboratory data, radiological reports, patient chart summaries, autopsy reports) must be made available to the Sponsor (or designee) or governing Health Authorities, if requested, with due precaution taken to ensure patient confidentiality.

### 13.10. Record Retention

Regulatory authorities require that the Investigator retain copies of all files pertaining to the study (i.e., records of study article disposition, signed informed consent documents, electronic case report forms, all correspondence, dates of monitoring visits, and records which support them) for a period of 2 years following the date of marketing application approval of the drug, for the indication that is the subject of the study. If no application is filed, or the application is not approved for the indication under study, all files pertaining to the study are to be maintained for 2 years after the investigation is discontinued and governing regulatory agencies have been so notified. Study records must be stored in a safe and secure location permitting timely retrieval, if necessary. The Investigator must obtain written permission from the Sponsor prior to disposing of any records.

If the Investigator relocates, retires, or withdraws for any reason from the study, trial records may be transferred to an acceptable designee, such as another Investigator within the institution. The Sponsor (or designee), as well as the responsible IRB or Ethics Committee, must be notified of the identity of the individual assuming responsibility for maintaining the study records and the location of their storage.

### 13.11. Monitoring of the Study

The Sponsor has responsibility to governing regulatory authorities to take all reasonable steps to ensure the proper conduct of the study with respect to trial ethics, protocol adherence, and data integrity and validity.

This study will be closely monitored by representatives of the Sponsor (and/or designee) throughout its duration. Monitoring will be in the form of personal visits with the Investigator and his/her staff as well as any appropriate communications by telephone, telefax, mail, or e-mail transmission. The purpose of these contacts is to review study progress, Investigator and patient adherence to protocol requirements, and any emergent problems associated with the conduct of the study. The following points will be usually assessed during monitoring visits at the site:

- Required regulatory documentation
- Signed informed consent documents
- Patient accrual and follow up
- Study drug inventory records
- Investigator and patient compliance to the study protocol
- Concomitant therapy use
- AE documentation
- Data as accurate, complete, and verifiable when compared to source documents

The Investigator and study staff are expected to cooperate with monitors during such visits and provide them with all relevant study documents.

In addition, the study may be evaluated by Sponsor auditors (and/or designees) and government inspectors who must be allowed access to eCRFs, source documents and other study files. Sponsor reports will be kept confidential. The Investigator should promptly notify the Sponsor of any audits scheduled by any regulatory authorities, and promptly forward copies of audit reports.

As applicable, in accordance with the Health Insurance Portability and Accountability Act (HIPAA) and associated privacy regulations, patient authorization to use personally identifiable health information may be required from each patient before research activities. This Authorization document must clearly specify what parties will have access to a patient's personal health information, for what purpose, and for how long.

### 13.12. Patient Confidentiality

Every effort will be made to maintain the anonymity and confidentiality of patients during this clinical study. Coded patient identifiers will be utilized at all times (including in any publications) when referring to a particular patient. However, because of the experimental nature of this treatment, the Investigator agrees to allow representatives of the Sponsor, or their designee, as well as authorized representatives of the governing regulatory agency, to inspect the facilities used in this study and to inspect, for purposes of verification, the hospital or clinic records of all patients enrolled into this study. A statement to this effect should be included in the informed consent document.

### 13.13. Financing and Insurance

The study will be supported by the Sponsor. Specifics of the financing and insurance coverage will be addressed in the clinical study agreement between the Sponsor and the Investigator or Institution.

#### 14. STATISTICAL ANALYSIS AND REPORTING OF DATA

### 14.1. Statistical Considerations

The primary objectives of the Phase 1a portion of this trial are to assess the safety, tolerability, DLTs, and, if feasible, the MTD of AVID100 when administered by 2-hour\* IV infusion to patients with a histologically-documented, measurable or non-measurable, locally advanced or metastatic solid tumor malignancy of epithelial origin that is refractory to standard therapy or for which no standard therapy is available. These effects will be assessed by treating patient cohorts with sequentially escalating doses of AVID100. Other studies to be conducted during this trial include characterization of the pharmacokinetic profile of AVID100, and description of the preliminary antineoplastic activity of AVID100 in these same patient cohorts.

In addition, once the MTD is identified, the Phase 2a portion of the trial will enroll patients to 3 expansion cohorts of patients (approximately 60 patients total) with advanced (unresectable or metastatic) malignancies of epithelial origin (tumor types mTNBC, SCCHN, and Sq-NSCLC), and confirmed as expressing the EGFR and with measurable disease, will be entered to further evaluate tolerability and assess the preliminary antineoplastic activity of AVID100 in this patient population.

Data on safety and preliminary activity collected from additional patients added to the Phase 2a expansion cohorts will be summarized with patients treated at that same dose level in the Phase 1a portion of the trial. No tests of statistical inference will be performed.

\*Protocol v5.0: Extended from 1 hour to 1.5 hours due to Grade 3 IRR observed in Cohort 3 (80 mg/m²); effective 20Jul2017 and documented in a study Note to File dated 21Jul2017 (see **Section 2.3.2.1**; AVID100-01: Clinical Experience)

\*Protocol v6.0: Extended from 1.5 hours to 2 hours due to Grade 2 IRRs observed in Cohort 4(120 mg/m2); effective 21Dec2017 and documented in a study Note to File dated 28Dec2017 (see **Section 2.3.2.1**; AVID100-01: Clinical Experience)

# 14.2. Sample Size Considerations

Sample size for the Phase 1a dose escalation portion of the study will be determined by safety observations, occurrence of DLTs, and the number of cohorts required to evaluate safety and choose an RP2D. It is assumed that approximately 4 cohorts will be required to determine the MTD, thereby enrolling approximately 14-30 patients during the dose escalation phase of the study. However, the protocol allows for enrollment of > 4 cohorts, should this be necessary to identify the MTD.

Sample size for the Phase 2a Expansion Cohorts will be approximately 60 patients treated at the RP2D, with accrual to be divided among up to 3 cohorts (tumor types mTNBC, N=30; SCCHN, N=15; and Sq-NSCLC, N=15; all approximations); additional patients may be entered to the Phase 2a Expansion Cohorts if fewer than 30 patients are required to establish the RP2D in Phase 1a.

The current planned initial enrollment of 15 patients per cohort (or cohort subgroup in the case of mTNBC) may be expanded based on initial observation of > 2 objective responses (13% ORR) in any of the three indications to be studied. This sample size has a 35.2% power to detect a 40% ORR compared to a potential control response of 20% at a two-sided 0.05 level of significance (TABLE 5). In addition, the power is between 45-54% to detect objective response rates between 20 to 40% in a 15 patient cohort at a two-sided 0.05 level of significance (TABLE 7).

After evaluation of the initial ORR in each cohort a decision will be made to either continue to include patients with treatment-refractory advanced/metastatic malignancies without other therapeutic options on an open-label trial(e.g., if the objective response rate is  $\geq 20\%$  and responses are durable), consider alternative trial designs for further exploration of efficacy in any of the indications, or discontinue development if fewer than two (0 or 1) responses are observed in any of the three initial fifteen patient cohorts. The durability of objective responses and disease stabilization > 8 weeks will also be considered in the decision to expand cohorts or pursue other options for further development in any of the three indications (TABLE 4). See also **Appendix I**.

TABLE 5: TEST OF NULL AT 0.05 LEVEL (TWO SIDED) USING NORMAL APPROXIMATION Power (%) for specified N (Computed using EAST 6.4)												
Null (π 0 )	Null $(\pi_0)$ True $(\pi)$ N=15 N=20 N=34 N=40											
0.20	0.30	13.2	16.3	24.6	28.1							
	0.40	35.2	44.7	66.3	73.3							
	0.50	64.2	76.5	93.8	96.7							
	0.60	88.5	95.5	99.7	99.9							

TABLE 6: SMALLEST VALUE OF P (%) FOR STATISTICAL SIGNIFICANCE (Level 0.05, 2-Sided)													
πο	π 0 N=15 N=20 N=34 N=40												
0.20	45.2	41.7	36.2	35.0									
0.25	50.4	46.9	41.6	40.2									
0.30	55.2	51.9	46.8	45.5									
0.35	59.9	56.8	51.8	50.5									
0.40	64.3	61.4	56.7	55.5									
0.45	68.6	65.8	61.4	60.2									
0.50	72.6	70.1	66.0	64.9									

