# 3.3. Trial Design Summary

### **Patient Population and Objectives**

Approximately 90 male and female patients with documented solid tumor malignancies of epithelial origin that are locally advanced or metastatic, and either refractory to standard therapy or for whom no standard therapy is available, will be entered into this Phase 1a/2a, multicenter, open-label, dose-escalation, cohort study of AVID100, an anti-human EGFR monoclonal antibody (mAb) linked to the maytansinoid DM1.

The initial Phase 1a Dose-Escalation portion of the trial (approximately 30 patients) is designed to evaluate the safety and tolerability, as well as identify the DLT(s), MTD, and RP2D of sequential escalating doses of AVID100 (study drug), when administered to patients with tumors reasonably likely to express EGFR; secondary objectives include characterization of the PK profile of total antibody (AVID100 plus MAB100), AVID100, and DM1, as well as preliminary assessment of the antineoplastic activity of AVID100.

Once the MTD and/or RP2D is identified, 3 expansion cohorts of patients (approximately 60 patients total; approximately 30 patients in the mTNBC cohort\* distributed equally to enroll 15 patients to each of two cohort subgroups [i.e., either 3+ intensity in  $\geq$  50% of tumor cells or  $\geq$  2+ intensity in  $\geq$  75% of tumor cells], and 15 patients to each of the SCCHN and Sq-NSCLC cohorts) with measurable disease and confirmed EGFR-positive tumors will be accrued during the subsequent Phase 2a Dose-Expansion portion of the trial where the goal will be to further evaluate the safety, tolerability, and antineoplastic activity of AVID100 when administered at the RP2D; a secondary objective is to further characterize the PK profile of total antibody, AVID100, and DM1 (PK evaluation will be less extensive in Phase 2a when compared to Phase 1a). The tumor types to be evaluated in these expansion cohorts are mTNBC, SCCHN, and Sq-NSCLC.

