#### 6.3.3 Cohort Closure

The Sponsor (or designee) will be in communication with the sites when the target total enrollment for a cohort has been attained. Once recruitment to a cohort is completed, accrual to the cohort will be closed, and sites will be so notified in writing. Cohorts will remain closed to further accrual, unless a decision is later made by the Sponsor (or designee) to further expand that cohort, based on protocol-defined criteria.

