The current planned initial enrollment of 15 patients per cohort (or in each subcohort in the case of TNBC) may be expanded based on initial observation of > 2 objective responses (13% ORR) in any of the three indications (two separate cohorts in TNBC) to be studied. This sample size has a 35.2% power to detect a 40% ORR compared to a potential control response of 20% at a two-sided 0.05 level of significance. In addition, the power is between 45-54% to detect objective response rates between 20 to 40% in a 15 patient cohort at a two-sided 0.05 level of significance. After evaluation of the initial ORR in each cohort a decision will be made to either continue to include patients with treatment-refractory advanced/metastatic malignancies without other therapeutic options on an open-label trial (e.g., if the objective response rate  $\geq$  20% and responses are durable), consider alternative trial designs for further exploration of efficacy in any of the indications, or discontinue development if fewer than two (0 or 1) responses are observed in any of the three initial fifteen patient cohorts. The durability of objective responses

\* Computed lower limit is negative.

\*\* Not all observed proportions given above are possible for n=15 and n=34

and disease stabilization > 8 weeks will also be considered in the decision to expand cohorts or pursue other options for further development in any of the three indications.

TEST OF NULL AT 0.05 LEVEL (TWO SIDED) USING NORMAL APPROXIMATION								
	Power (%	) for specified N (	Computed using E	AST 6.4)				
Null (π 0 )	Null $(\pi_0)$ True $(\pi)$ N=15 N=20 N=34 N=40							
0.20	0.30	13.2	16.3	24.6	28.1			
	0.40	35.2	44.7	66.3	73.3			
	0.50	64.2	76.5	93.8	96.7			
	0.60	88.5	95.5	99.7	99.9			

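### Sections 14.2 and Appendix I: the Phase 2a expansion threshold gives a count (at least 3 of 15) and a percentage (13%, which is 2 of 15) that disagree, and the stop clause counts three 15-patient cohorts where there are four groups

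*Combined protocol and SAP*

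**What the plan says.** Section 14.2 sets the first activity look at "15 patients per cohort (or cohort subgroup in the case of mTNBC) may be expanded". The trigger is that enrolment "may be expanded based on initial observation of > 2 objective responses (13% ORR) in any of the three indications to be studied". Appendix I has the same trigger ("may be expanded based on initial observation of > 2 objective responses (13% ORR"), but describes the groups as "any of the three indications (two separate cohorts in TNBC) to be studied".

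Both places then introduce three courses of action. Section 14.2 opens this with "After evaluation of the initial ORR in each cohort a decision will be made". The courses are:
- continue open-label enrolment, with an ORR of at least 20% and durable responses given as an example;
- look at other trial designs, with no response count attached;
- "discontinue development if fewer than two (0 or 1) responses are observed in any of the three initial fifteen patient cohorts".

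Both places add that durability of response and stable disease beyond 8 weeks will be weighed.

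Section 3.3 describes the mTNBC cohort of about 30 patients as "distributed equally to enroll 15 patients to each of two cohort subgroups", with 15 more in each of the SCCHN and Sq-NSCLC cohorts. Under Section 6.3.3 a closed cohort stays closed "unless a decision is later made by the Sponsor (or designee) to further expand that cohort, based on protocol-defined criteria".

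**The concern.** A decision rule on 15 patients is a rule about integers, and here the integer is given in two ways that differ by one. A reader who trusts the count needs 3 responses before expanding a group. A reader who trusts the percentage needs 2. The rest of the paragraph does not break the tie, because the stop zone supports one reading and the 20% example supports the other. At 2 of 15, one reader would say that the group may be expanded and another that it belongs with the alternative designs. Neither would stop it.

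The stop clause has a separate counting error. Three fifteen-patient cohorts matches neither the three tumour cohorts (about 30, 15 and 15 patients) nor the four groups of 15. The expansion sentence allows for the mTNBC split, but the stop clause does not.

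What is at stake is consistent handling of each group when its first 15 patients are assessed, and Section 6.3.3 relies on criteria defined in the protocol for reopening a cohort. No endpoint, estimate or test is affected.

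**Working it through.** **Inputs.** Group size 15 (14.2, Appendix I). Trigger printed as more than 2 responses and as 13% (14.2, Appendix I). Stop zone of 0 or 1 (14.2, Appendix I). Continue example of ORR at least 20% (14.2, Appendix I). Control rate 20% and alternative 40% (14.2). The 10% and 30% rates are added here as assumptions, to show the range.

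**The plan's own figure.** The stated power of 35.2% at n = 15, 40% against 20%, reproduces with the Appendix I statistic (variance at the true rate):

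Φ(√15 × (0.40 − 0.20)/√(0.40 × 0.60) − 1.96) = Φ(1.581 − 1.960) = Φ(−0.379) = 35.2%.

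This power belongs to a significance test that needs at least 45.2% observed (Table 6), that is 7 of 15 (46.7%). It does not depend on the expansion trigger and does not help to choose between the two readings.

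**Count against percentage.** 1/15 = 6.7%, 2/15 = 13.3%, 3/15 = 20.0%. More than 2 starts at 3, or 20.0%. The printed 13% is 2.

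**What the neighbouring clauses imply.**
- Stopping at 0 or 1 leaves 2 and above, which is exactly the complement of a threshold of 2.
- Continuing at 20% or more is 3 and above, which is exactly a threshold of 3.
- The middle option has no count, so it could hold 2 of 15 or nothing in particular.

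**Size.** Let X be the number of responders, binomial with n = 15 and true rate p. Then P(X = 2) = 105 p²(1 − p)¹³ and P(X ≥ 3) = P(X ≥ 2) − P(X = 2). At p = 0.20, P(X ≤ 1) = 0.167, so P(X ≥ 2) = 0.833; P(X = 2) = 105 × 0.04 × 0.8¹³ = 0.231; and P(X ≥ 3) = 0.602.

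| True ORR | P(exactly 2) | Count met if 3 needed | Count met if 2 needed |
|---|---|---|---|
| 10% | 27% | 18% | 45% |
| 20% | 23% | 60% | 83% |
| 30% | 9% | 87% | 96% |
| 40% | 2% | 97% | 99.5% |

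**Number of groups.** Two mTNBC subgroups of 15, plus SCCHN 15, plus Sq-NSCLC 15, gives 4 × 15 = 60. This agrees with the planned Phase 2a total of about 60.

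**The case against.** The strongest objection is that the sign may simply have been lost. If the PDF prints an underlined 'greater than', the trigger is 2 or more, 13% is right, and it complements the stop zone. What then remains at 2 of 15 is a soft overlap with the alternative-designs option. Inequality signs do vary elsewhere in the document: the QTc exclusion in the synopsis and in Section 4.3.1 is one case, and the MTD percentage in the synopsis and in Section 6.9 is another. This is possible but not shown. The same sign appears in both places, and both print the greater-or-equal sign for the 20% example. It is the first thing to check.

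A second defence is that 13% merely translates the number 2, the value to be exceeded. Then 3 is the threshold and 2 of 15 falls to alternative designs. That is coherent, but no text says so.

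Third, the rule is soft. Expansion is permitted rather than required, Section 4.1.2 leaves expanded accrual to the sponsor, durability and stable disease are also weighed, and Section 14.2 separately allows extra patients if Phase 1a needs fewer than 30. Section 14.1 plans no inferential tests. All of this stands and limits the importance of the point. It does not make the threshold readable.

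On the stop clause, a reader might infer from the word 'any' that one failing group ends the whole programme. The documents do not support that reading. The sentence starts from the ORR in each cohort, and the same text uses 'any' distributively for expansion and for further development by indication. Recruitment to the mTNBC subgroups is also paused at 15 to assess activity. What stands is the wrong count of three and the missing mention of the subgroups.

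**Conclusion.** The point holds as a minor wording correction to a decision threshold. As printed, count and percentage disagree in both places, and the handling of 2 of 15 is not determined. The documents do not settle whether 2 or 3 is intended, so neither should be presumed.

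The difference matters at low to moderate activity, with 27 percentage points in the chance of meeting the count at 10% ORR (45% − 18%) and 23 at 20% ORR (83% − 60%). It hardly matters at the 40% alternative. These figures assume 15 response-evaluable patients per group, independent responses and a common true rate within the group. They describe meeting the count, not the sponsor's final decision.

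A reader might also infer an error-rate problem. There is none: no test depends on the trigger, and the 35.2% power is unaffected by it. The count of three fifteen-patient cohorts is wrong on the plan's own design, which has four groups of 15. Confidence in the trigger part depends on the sign in the source PDF.

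**What to change.** First check the inequality sign in the source PDF. Then, in both Section 14.2 and Appendix I:

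1. The sponsor confirms the intended integer and makes count and percentage agree: either at least 2 of 15 (13%) or at least 3 of 15 (20%).
2. State what happens at exactly 2 of 15.
3. Replace the reference to three fifteen-patient cohorts in the stop clause with wording that applies to that cohort or mTNBC subgroup. If stopping the whole programme on one group is really meant, say so explicitly.

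This changes wording in two places. It needs no extra patients, procedures or analyses and leaves the sponsor's discretion as it is. If the confirmed integer differs from the one the sponsor has been working with, the chance of meeting the count changes as in the table, so the choice should be a deliberate one.

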There is potential for additional expansion cohorts within the Phase 2a portion of the trial (by amendment only).

Expanded accrual in any cohort will take place at the Sponsor discretion, after discussion with the Investigator(s).

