#### **Response Calculations**

In the event of an OR (CR or PR) the duration of the OR will be determined from the day the initial response is observed (using screening/baseline images for comparison) to the day that progression is observed. Duration of SD (minimum duration of not less than 8 weeks) will also be assessed using the time from the first dose of AVID100 to the day that PD is documented.

The ORR will be calculated as the proportion of patients who achieve either a complete response or a partial response (CR+PR). ORR, time to OR, and duration of OR will be determined.

DCR will be calculated as the proportion of patients who achieve either a complete response, partial response, or disease stabilization for a minimum of 8 weeks (CR+PR+SD).

TTP will be measured from the treatment start date (date of first dose) to either the date the patient is first recorded as having disease progression (even if the patient went off treatment because of toxicities), or the date of death if the patient dies due to any cause before progression. If a patient is lost to follow-up, the patient will be censored as of the date of last contact. Patients who start a new treatment before they progress will be censored as of the date of start of the new treatment. If a patient has not progressed nor died, time to progression is censored at the date of last follow-up. TTP will be analyzed using the method of Kaplan and Meier.

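### In a Phase 2a cohort expanded because its first 15 patients responded, the plain pooled ORR is biased upward, and the plan does not report ORR by stage

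*Combined protocol and SAP*

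**What the plan says.** Section 14.2 sets a "planned initial enrollment of 15 patients per cohort (or cohort subgroup in the case of mTNBC"), which "may be expanded based on initial observation of > 2 objective responses"; it glosses this count as a 13% ORR. At the other end, the sponsor may "discontinue development if fewer than two (0 or 1) responses are observed in any of the three initial fifteen patient cohorts". Appendix I repeats these rules, and Sections 3.3 and 4.2 say that mTNBC subgroup recruitment stops at 15 so that activity can be assessed.

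The rule is not mechanical. Section 14.2 adds: "The durability of objective responses and disease stabilization > 8 weeks will also be considered in the decision to expand cohorts". Section 4.1.2 says: "Expanded accrual in any cohort will take place at the Sponsor discretion, after discussion with the Investigator(s"). There is also a route to extra patients that has nothing to do with response: "additional patients may be entered to the Phase 2a Expansion Cohorts if fewer than 30 patients are required to establish the RP2D" in Phase 1a.

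For the analysis, the Response Calculations part of Section 14.3.3.1 says: "The ORR will be calculated as the proportion of patients who achieve either a complete response or a partial response (CR+PR"). The Phase 2a part of that section presents ORR as counts and percentages and names a confidence interval only for TTP. Section 14.1 states that Phase 2a data are summarized together with Phase 1a patients at the same dose and that no inferential tests are planned. Nothing in the document splits ORR at the 15-patient look, adjusts for it or warns of it. Section 14.3 leaves detailed methods to a separate SAP, to be final before database lock.

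**The concern.** If the first 15 patients decide whether more are enrolled, their response count has been selected for being high in any cohort that goes on. Pooling those 15 with later patients and taking a simple proportion carries the selection into the reported ORR. Antineoplastic effect is part of the primary Phase 2a objective, and Section 14.2 makes ORR the main input to what happens next, giving an ORR of at least 20% as its example of a reason to continue. The inflation is largest when the drug is weak, which is where a wrong decision to go on is most likely.

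**Working it through.** **The plan's own figure.** Section 14.2 gives 35.2% power at N=15 for 40% against 20%. With the variance taken at the true rate, power = Φ(√15 × 0.20/√(0.40 × 0.60) − 1.96) = Φ(1.581 − 1.96) = Φ(−0.379) = 35.2%. It reproduces, and it treats the 15 patients as a fixed sample.

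**Inputs.**
- First stage n₁ = 15 (Section 14.2).
- Trigger c: more than 2 responses means c = 3, or 3/15 = 20%. The 13% printed beside it is 2/15, so c = 2 is also shown.
- Final size N: not stated. Assumed 20, 34 or 40, the larger columns of Table 5.
- True ORR p: assumed 10% to 40%, the same before and after the look.
- Expansion assumed to follow the trigger exactly.

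**Formula.** X₁ ~ Bin(15, p). Mean pooled ORR given expansion = (E[X₁ | X₁ ≥ c] + (N − 15)p)/N.

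**Worked case, p = 20%, c = 3.** P(X₁ = 0, 1, 2) = 0.0352, 0.1319, 0.2309, so P(expand) = 0.602. E[X₁ | expand] = (3 − 0.1319 − 2 × 0.2309)/0.602 = 2.4063/0.602 = 3.997, which is 26.6% of 15. At N = 20: (3.997 + 5 × 0.20)/20 = 25.0%. At N = 40: (3.997 + 25 × 0.20)/40 = 22.5%.

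**Bias of the pooled ORR given expansion, c = 3 (percentage points).**

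| True ORR | P(expand) | Mean ORR, first 15 | N=20 | N=34 | N=40 |
|---|---|---|---|---|---|
| 10% | 0.18 | 22.6% | +9.4 | +5.5 | +4.7 |
| 20% | 0.60 | 26.6% | +5.0 | +2.9 | +2.5 |
| 30% | 0.87 | 32.7% | +2.0 | +1.2 | +1.0 |
| 40% | 0.97 | 40.8% | +0.6 | +0.3 | +0.3 |

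With c = 2 the bias at N = 20, 34 and 40 is +5.3, +3.1 and +2.7 at a true 10%, +2.2, +1.3 and +1.1 at 20%, and about +0.1 at 40%.

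**Averaged over stopped and expanded cohorts** the same proportion is biased downward: at a true 20%, c = 3, by −1.0, −2.2 and −2.5 points at N = 20, 34 and 40.

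**Which correction goes the right way.** Take 7 responses in 34, c = 3; the plain figure is 7/34 = 20.6%. Given expansion and a total of 7, X₁ takes values 3 to 7 with weights C(15, x)·C(19, 7 − x), and its mean is 3.719.
- The estimator unbiased conditional on expansion is the expected second-stage proportion: (7 − 3.719)/19 = 17.3%.
- The standard two-stage UMVUE is the expected first-stage proportion: 3.719/15 = 24.8%. It is unbiased only over stopped and expanded cohorts together. Given expansion, its mean is that of the first 15 alone (22.6% at a true 10%, 26.6% at 20%) whatever N is.

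Other conditional estimates: 8/40 goes from 20.0% to 17.1%, and 14/34 from 41.2% to 41.1%.

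**The case against.** The strongest reply is that the plan contains no strict two-stage rule. Expansion is permitted rather than required, durability and stable disease are weighed too, and the sponsor has discretion. Patients may also be added through unused Phase 1a places; Table 1 lists 24 Phase 1a patients against the 30 allowed for, so that route appears open. All of this stands. A reader might infer that every enlarged cohort reports too high an ORR. The documents do not support that, because a cohort enlarged without regard to response carries no such bias. Even after response-based expansion the bias is an average: at a true 20%, c = 3, the pooled ORR exceeds the truth in 72% of expanded cohorts at N = 34 and 57% at N = 40.

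A second reply is that pooling is inferred. The ORR definition is generic, and a fuller SAP is to follow. A reader might take the N = 20, 34 and 40 columns of Appendix I as the planned analysis of expanded cohorts, but the appendix offers them as fixed-sample considerations and does not label them so. What remains is that a plain proportion over a cohort's patients is the natural reading of Section 14.3.3.1, and nothing provides a split.

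Third, activity is called preliminary and no tests are planned. A reader might infer an inflated false-positive rate; no error rate is defined here to inflate. A descriptive estimate can still mislead a development decision.

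Finally, at the 40% rate used in the power statement the bias is under 1 point, and over all cohorts it is downward. Both are true. Neither corrects the figure shown for a cohort that expanded on response when the true rate is about 10% to 20%.

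**Conclusion.** The concern holds for cohorts or mTNBC subgroups expanded because of response in the first 15 patients. There, the plain pooled ORR is biased upward given expansion: by an amount that matters at true rates of 10% to 20%, modestly at 30%, and negligibly at 40%. The sizes shown rest on an assumed final N of 20 to 40, a trigger of 3 or more of 15, a constant true rate and a rule followed exactly. A lower trigger roughly halves them at 10% and 20%. Because the actual decision is partly discretionary, its true bias cannot be computed, which is a reason to show the stages separately. This is a reporting weakness in a descriptive analysis and does not invalidate the design.

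**What to change.** In Section 14.3.3.1, and in the SAP when it is written, add that for any cohort or subgroup expanded after the 15-patient look, ORR with an exact 95% confidence interval will be reported separately for the first 15 patients and for those enrolled after the decision, beside the pooled figure. State that the pooled figure is selected on first-stage response, and the first-15 figure more strongly so. The post-decision figure is free of that selection.

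If one adjusted number is wanted, name an estimator that is unbiased conditional on expansion and do not use the standard two-stage UMVUE. That option needs the trigger and the number of added patients fixed before the look, so Section 14.2 would have to settle whether the trigger is 3 responses or 2.

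The cost is a few lines of text, extra table rows and minor programming. The post-decision estimate is less precise because it uses fewer patients (5 to 25 under the sizes assumed here), and a conditional estimate will come out somewhat lower for a weak drug while barely changing for an active one.
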